Adherence, or "sticking to your diet" is important for successful initial weight loss and keeping off the weight over the long term (1). While early behavioral and dietary adherence have been associated with greater weight loss, sticking to a diet plan is difficult. It is not clear if adherence to any diet plan (even one which does not produce weight loss) is hard or whether people who are overweight have more difficulty with adhering to diet plans compared to people who are relatively lean.

The main aim of this study is to evaluate dietary adherence in 3 groups of individuals participating in a 6-week heart-healthy dietary intervention program. Two groups [1. Lean (BMI < 25 kg/m²) and 2. Obese (BMI ≥ 30 kg/m²)] will receive a heart-healthy diet designed to maintain their weight, and the third group [3. Obese] will be given a heart-healthy diet that is 35% *less* than their daily calorie needs to lose weight. Participants will attend one counseling session per week and will be contacted randomly 1x/week by study staff for completion of a 24-hour dietary recall. They will complete daily food diaries and daily records using smart-phones. Prior to starting the assigned heart-healthy dietary intervention, participants will complete questionnaires that include questions about how motivated they are to follow a diet, lose weight, and change eating patterns. These findings may help us understand what factors affect adherence, and help us design weight loss studies that improve people's ability to stick to diet interventions.

A. INTRODUCTION

Obesity, defined by the NHLBI in 1998 (2) as a body mass index [BMI, in kg/m^2] > 30 , has become a medical epidemic in the US (3), and is reaching pandemic proportions in most industrialized countries. Obesity is linked to a number of medical complications and is a leading cause of preventable death in America, contributing to over 150,000 excess deaths per year (4). At any given time of the year, between 15 and 35% of the adult population in the US is reportedly attempting to lose weight (5), yet, successful weight reduction and maintenance of weight loss remain elusive goals for many dieters. In fact, a relatively small maximum average weight loss is common even in very low calorie long-term treatments (6). This low treatment efficacy has been consistently observed, and while some do achieve weight loss success, only about 20% of overweight individuals maintain the weight loss (7).

Adherence is defined as the "extent to which patients follow the instructions that are given to them for prescribed treatments" and is intended to be non-judgmental, a statement of fact rather than of blame of the patient, prescriber, or treatment (8)." Adherence is widely recognized as essential for achieving successful health outcomes yet non-adherence is the primary treatment barrier for most medical conditions. A recent review found that rates of non-adherence to treatment recommendations are 20%-40% for acute conditions, 30% to 60% for chronic conditions and 80% for prevention (9). Rates of non-adherence are substantially lower for lifestyle prescriptions and other more behaviorally demanding regimens (10). Lack of adherence is a pervasive problem in clinical research. This lack of adherence to assigned interventions results in intention to treat analyses, which are biased towards null findings (11).

For the treatment of obesity, there is a consensus that adherence is critical for successful initial weight loss and long term weight maintenance (1). Many studies have sought to identify

predictive demographic, psychosocial and behavioral characteristics that lead to weight loss success and successful weight loss maintenance. Age, income, marital status, ethnicity, employment status, previous dieting and weight history, dietary restraint, binge eating disorder, self-motivation and familial support, early weight loss success, and weight loss expectations are among the multitude of variables that have been studied (12). Ultimately, poor adherence to calorie-reduced diets is one of the most plausible explanations for less than predicted weight loss in clinical studies. In one review, Heymsfield and colleagues (6) concluded that participant adherence to the prescribed diet was the most likely explanation for the observed low efficacy of low-calorie diets, even after considering metabolic adaptations. Another recent study comparing four popular diets found a highly significant relationship between self-reported dietary adherence and weight loss, such that participants who scored in the top third of adherence lost an average of 7% of body weight. However, no single diet produced satisfactory adherence rates and the progressively decreasing mean adherence scores over time were practically identical among the 4 diets (13).

Factors predicting adherence have been moderately studied. Cognitive skills, the underlying brain skills that make it possible for individuals to think, remember and learn, have recently been found to predict adherence (14-16). To examine neuropsychological and cognitive factors, traditional neuropsychological tests and measures designed to stimulate real-world situations (everyday cognitive measures) are often administered. Poor neurocognitive performance as measured by various neuropsychological performance tests, has been associated with decreased medication adherence in many clinical populations, including HIV, type II diabetes, older adults and individuals taking antidepressants (14).

The neuropsychological factors which are most predictive of medication non-adherence are poor executive functioning (necessary for goal-directed behavior e.g. ability to initiate/stop actions, monitor/change behavior, plan future behavior, anticipate outcomes, think abstractly), followed by working memory (availability of information needed to complete immediate and short-term tasks) and processing speed (a measure of learning and thinking efficiency) (14). Poor performance on an everyday problem solving questionnaire was associated with poorer self-reported medication adherence (14). Moreover, problem-solving skills as measured by the Social Problem Solving Inventory partially mediated the relationship between treatment adherence and weight loss outcome in one recent study (15) and were significantly related to greater overall weight loss and long term weight loss maintenance in another study (16). In addition to evidence relating cognitive skills to adherence and weight loss, recent observations support a relationship between obesity status and performance on tests measuring decision-making (17;18) (Iowa Gambling Task), problem solving and working memory (Wisconsin Card Sorting Task) and inhibition/attention (Go/No Go task; (19)).

Personality is another factor significantly influencing health. The most common relationship between these variables is based on the Five Factor Model dimensions (FFM; (20)) - Neuroticism, Extraversion, Openness, Agreeableness and Conscientiousness, which are empirically derived clusters that capture the major axes of psychological and behavioral variation in humans (21;22). FFM factors have been linked with many health-related behaviors and outcomes, including medication non-adherence. One recent study found that neuroticism was the second strongest predictor of non-adherence to CPAP treatment for obstructive sleep apnea (23). Previous studies have shown that medication non-adherence (24) as well as emotional and external eating behaviors (25) were most frequently associated with lower levels of

Conscientiousness and higher levels of Neuroticism. However, no study to date has measured FFM with weight loss and/or dietary adherence.

Successful weight management appears to require adherence across a wide variety of behaviors yet measuring adherence poses a significant problem. While objective behavioral measures are superior to subjective self-report measures, objective measures are often difficult to obtain. Both early behavioral (e.g. attendance) and self-reported dietary adherence were predictors of changes in body weight, waist circumference and body fat, but for dietary adherence the magnitude of the effect was smaller (26). It is widely accepted that adherence to weight management strategies is critical for successful weight loss and for long-term maintenance (1). However, it is not clear whether problems with adherence occur more frequently with diets to promote weight loss versus weight maintenance, any diet prescription, and whether increased adiposity might in itself predispose to more difficulty with dietary and behavioral adherence. Our study aims to address these questions.

Summary:

Adherence is essential for initial weight loss and long-term weight maintenance. It is unclear whether adherence to dietary protocols differs between lean and obese individuals and whether non-adherence is specific to weight loss intervention diets (compared to weight maintenance diets). Several predictors of adherence to medical treatments have been described, including associations with memory, problem solving, neuropsychological factors, personality traits and levels of motivation. To understand how adherence may differ by adiposity and diet, we will examine differences in dietary adherence between lean and obese individuals and within the obese group between those prescribed a heart-healthy weight maintenance versus reduced calorie

diet. We will also examine predictors of adherence and the relationship between dietary adherence and weight loss.

B. AIMS

The primary goal of the current study is to determine whether or not there are differences in dietary adherence between lean and obese individuals and between two groups of obese individuals assigned different heart-healthy dietary prescriptions (weight maintaining diet [WMEN] vs. underfeeding [UF]). Thus 3 groups will be compared:

1. Lean WMEN
2. Obese WMEN
3. Obese UF

The secondary aim is to:

1. Examine predictors of adherence in general (e.g. motivation, self-efficacy, social support, personality traits, stress, neuropsychological/cognitive factors)

C. HYPOTHESES

The primary hypothesis for the study is that:

1. Adherence to a heart-healthy dietary intervention will be greatest in the lean WMEN group, followed by the WMEN obese group, and subsequently lowest in the UF obese group

The secondary hypotheses are that:

1. Within the UF group, individuals with higher adherence scores will lose more weight than those with lower scores

2. Poor performance on neuropsychological tests and problem solving questionnaires will be associated with decreased adherence across all groups
3. Higher levels of neuroticism will be associated with lower levels of dietary adherence in all 3 groups
4. Higher levels of motivation and self-efficacy will predict greater adherence

D. RESEARCH DESIGN & METHODS:

Study Design: This is a study of lean and obese individuals undergoing a 6-week heart-healthy dietary intervention to examine dietary adherence. This design will allow us to determine whether or not levels of adherence are different between lean and obese individuals as well as between obese individuals receiving weight maintenance energy needs and those being underfed. Findings will also help us determine factors that influence dietary adherence.

1. Subjects and Recruitment: Non-diabetic individuals aged 18-70 years who are in good health and living in the greater Phoenix, AZ, metropolitan area are eligible to participate in this study. All subjects will be fully informed of the methods and risks of the study prior to giving written informed consent. Consent will be obtained by the principal investigator, co-investigators, study physicians or physician assistant, who will be well informed about the protocol and the intervention. Subjects will also be specifically advised that the results of testing for drug usage will be filed in the medical record and would, therefore, be available as part of this record. We do not plan or anticipate the enrollment of non-English speaking subjects; however they are not excluded from participation either. Should a non-English speaking subject be eligible for enrollment, IRB approval will be obtained for use of the short form consent

process in the absence of a fully translated consent document as outlined in SOP 12.9.1, under the provisions of 45 CFR 46.117(b)(2). IRB approval will be obtained according to IRB guidance prior to obtaining informed consent from the potential study participant/s.

Subject recruitment for this study will be through advertisement in local newspapers and through postings of the included flyers in various public places such as, but not limited to, libraries, public universities, hospitals, health clubs, and local health fairs. Additionally, advertisements may be placed in some national newspapers or websites (Craigslist) to reach a wider audience, particularly for the lean, weight-maintaining arm of the study. We aim to recruit 50% women for each study arm. A review of previous enrollment in our studies indicates that we typically have an even distribution of ethnic groups in our study samples (e.g. control versus treatment) even when the representation of ethnic categories is not equal. Thus, we expect to have at least 33% of volunteers represented by African American, Hispanic, Asian, or Native American groups in each of our study arms. We plan to enroll 60 individuals and in order to enroll this many, we will likely need to screen many more. We have therefore set our anticipated number to be screened at 180, equal to three times the number enrolled. For randomization, we will stratify the groups by gender and age, using a block design.

2. Inclusion Criteria:

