1. BMI
 - a. $\text{BMI} \geq 30 \text{ kg/m}^2$ for the obese WMEN and UF groups but body weight less than 350 pounds to accommodate the DXA scanner
 - b. $\text{BMI} \leq 25 \text{ kg/m}^2$ (and $\text{BMI} \geq 18.5 \text{ kg/m}^2$) for the lean WMEN group

2. Age ≥ 18 years. Minors under the age of 18 will be excluded because growth and pubertal issues are significant parameters that could affect our outcomes and also because the time requirements of the study are such that they would interfere with school schedules.
Participants must be healthy, as determined by medical history, physical examination, and laboratory tests.
3. Weight stable ($\pm 2\%$) for last 3 months

3. Exclusion Criteria:

Candidates will be screened by phone to exclude those with BMI ≥ 26 kg/m² and BMI ≤ 29 kg/m², significant health problems, including cancer, hypertension, diabetes, current and past 3-month use of certain prescribed medications, especially those that could affect body weight, such as antidepressants and stimulants as well as smoking, or excess alcohol (> 3 drinks/d). Women must not be pregnant or lactating, and be at least 1 year postpartum. Candidates with a history of psychotic disorder or hospitalization for psychiatric illness within the past 1 year will not be eligible. They will need to be weight stable for the past 3 months ($\pm 2\%$) and cannot be in treatment for obesity or currently receiving psychotherapy. Individuals who meet criteria according to the phone screen will be invited to come to the unit for a screening visit and their screening sheets are placed in a locked filing cabinet. Forms from potential volunteers who are ineligible are shredded.

4. Experimental Design:

Screening visit: Participants will arrive on the unit in a fasting state. Written informed consent will be obtained from the participant prior to any screening visits, study procedures or

treatments. The Principal Investigator or other designated qualified protocol investigators (listed on the protocol face page) will explain the study in language understandable to the subject.

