For our primary hypothesis, a one-way ANOVA will be performed with total adherence score as the dependent variable and group status (lean WMEN, obese WMEN, obese UF) as the independent variable. In addition, linear regression models adjusted for covariates including age, sex, race, socioeconomic status (SES) and baseline weight or percent body fat will also be used to examine the relationship of adherence and behavioral factors. Correlations between adherence scores, behavioral test scores and weight, fat mass and fat free mass loss will be calculated. Pearson's r will be calculated for data that are normally distributed and Spearman's correlation will be used if the distributions are non-normal. This will be an intention to treat study such that everyone who completes the run-in phase will be included in the final analysis. Missing data will be completed using a multiple imputation method utilizing the SAS procedures, PROC MI and MIANALYZE. This method introduces variability into the imputed values to reduce the risk of a type 1 error. All tests will have a 2-sided Type I error of $p = 0.05$.

Power Calculation:

Sample size calculations are based on the number of individuals needed to demonstrate a significant difference in adherence scores over the 6-week intervention period between the 3 diet groups (lean WMEN, obese WMEN, obese UF).

We based our expected percent adherence score on a recent paper by Williamson et al (26) who observed 52% adherence in a group of obese dieters. Our maximum possible adherence score is 21 per week. To account for the increased adherence we expect to see because food is being provided in the study, we have increased the proposed adherence from the 52%

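### The primary ANOVA omits the stratification factors sex and age, and no adjusted analysis is named for the lean-versus-obese comparison, which is observational

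*Combined protocol and SAP*

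**What the plan says.** - Section D.1 (Subjects and Recruitment): "For randomization, we will stratify the groups by gender and age, using a block design". The same section aims for half women in each arm and expects an even ethnic spread across arms.
- Section D.2 (Inclusion Criteria) separates the groups by BMI. A BMI of 30 or more is required "for the obese WMEN and UF groups but body weight less than 350 pounds to accommodate the DXA scanner"; a BMI of 18.5 to 25 is required "for the lean WMEN group".
- Section B (Aims) makes it part of the primary goal to learn "whether or not there are differences in dietary adherence between lean and obese individuals". Section A asks "whether increased adiposity might in itself predispose to more difficulty with dietary and behavioral adherence".
- Section D.6 (Statistical Analysis), primary hypothesis: "a one-way ANOVA will be performed with total adherence score as the dependent variable and group status" as the independent variable. No other term is listed.
- The next sentence of D.6 adds "linear regression models adjusted for covariates including age, sex, race, socioeconomic status (SES) and baseline weight or percent body fat", which "will also be used to examine the relationship of adherence and behavioral factors".
- Section D.4 (Psychological Assessment) allows questionnaire scores to serve as covariates, but ties none to the primary test.

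**The concern.** Two things are missing from the primary analysis, and they differ in weight.

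**Strata.** Factors used to stratify randomisation normally belong in the model. If they predict the outcome and are balanced by design, leaving them out puts their variance into the error term. The test then becomes conservative and loses power, in a trial whose stated power is just under 0.80.

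**Lean versus obese.** A participant cannot be randomised to a BMI class, so only obese WMEN versus obese UF is a randomised contrast. Blocked randomisation cannot balance the lean group against the other two. If lean volunteers differ in age or SES, and these relate to adherence, the comparison carries that difference. It could create an apparent effect of adiposity or hide a real one. Section A asks about adiposity in itself, which an unadjusted comparison of self-selected groups cannot isolate. D.6 neither labels this contrast as observational nor names an adjusted version of it.

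**Working it through.** **Inputs from the plan (D.6 and Table 3A).** Means 13, 16, 19; SD 6; 20 per group; alpha 0.05; stated power 0.793. **Assumed, because the documents give no figure:** the share of outcome variance explained by covariates (R²), and the size of any covariate difference between lean and obese.

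**1. Reproduce the stated power.** Squared deviations of the means from 16 sum to 9 + 0 + 9 = 18. (The text of D.6 gives 32 for this sum, but the printed power follows from the means.) Noncentrality = 20 × 18 / 36 = 10. Noncentral F with 2 and 57 df gives 0.7933, in agreement with 0.793.

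**2. Add sex and age.** Error df = 57 − 2 = 55; noncentrality = 10 / (1 − R²).

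| Assumed R² | Noncentrality | Power |
|---|---|---|
| 0 | 10.00 | 0.792 |
| 0.05 | 10.53 | 0.814 |
| 0.10 | 11.11 | 0.835 |

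With three extra df (54) each power changes by less than 0.001.

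**3. Randomised contrast alone.** This was simulated with 20 against 20 obese participants, perfectly balanced over four sex-by-age cells (assumed; D.1 gives no age cut-points), 100,000 runs, R² 0.10. The true error rate of the unadjusted test is 0.038, against 0.050 adjusted. Power for a 3-point difference is 0.329 unadjusted and 0.369 adjusted. Error is not inflated.

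**4. Lean versus obese.** Suppose there is no true effect and confounding shifts the lean mean by b points. Squared deviations of (b, 0, 0) sum to 2b²/3, so noncentrality = 20 × (2b²/3) / 36 = 0.370 b², with 2 and 57 df.

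| Shift b (points) | Noncentrality | F test rejects |
|---|---|---|
| 0.5 | 0.093 | 5.7% |
| 1 | 0.370 | 7.7% |
| 2 | 1.481 | 17.0% |

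To link b to a covariate: b = 6 × √R² × d, where d is the lean-obese difference in covariate SDs. At R² 0.10, d = 0.5 gives b = 0.95 (7.5%), and d = 1 gives b = 1.90 (15.7%). For scale, ages spread evenly over the eligible 18 to 70 have SD 52/√12 = 15 years, so d = 1 would be a 15-year gap in age. A shift against the hypothesis costs power instead: at b = 0.95 the unadjusted power falls from 0.793 to about 0.64.

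**5. Which model removes the confounding?** Simulated with SES as the confounder (R² 0.10, lean shifted by 0.5 or 1 SD, no true effect):
- group only: rejects about 7% or 16%;
- group, sex and age: about 7% or 15%, essentially unchanged;
- group, sex, age and SES: about 5% in both cases.

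**The case against.** **An unadjusted ANOVA is valid for the randomised arms.** This stands. A reader might infer that ignoring the strata invalidates the primary test or inflates its error rate. Step 3 shows the opposite, so this half concerns efficiency only. No stated power figure is wrong.

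**Adjustment is already planned.** Partly right. D.6 lists age, sex, race and SES directly after the ANOVA, so it would be wrong to say that the plan ignores them. But those models have another stated purpose. Their covariate set also includes baseline weight or percent body fat, which largely defines lean and obese and would remove or destabilise that contrast.

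**The design limits imbalance.** Also partly right. The target for women and the expected ethnic spread leave mainly age and SES. All groups share the same health, smoking, alcohol, medication and weight-stability restrictions. If the stratification sentence in D.1 is meant to cover lean volunteers too, age may be partly handled, but the text does not say how. A reader might also infer different source populations from the wider advertising for the lean arm. That advertising is only optional, and D.1 limits every arm to greater Phoenix.

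**The error rates depend on assumptions.** This stands. A reader might take 16 to 17% as the expected false-positive rate. It needs a shift of about 2 points, for which the documents give no evidence. The rates are also for the three-group F test, since D.6 names no pairwise contrast.

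**A sex-and-age model does not cure SES confounding.** This stands; step 5 confirms it. Adjustment for SES helps only as far as SES is measured, and the instrument described in D.4 is a subjective ladder.

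**Conclusion.** The point holds in limited form. Omitting the strata biases nothing in obese UF versus obese WMEN. It forgoes perhaps 2 to 4 percentage points of power for the overall test (0.793 to 0.814 or 0.835 at an assumed R² of 0.05 or 0.10), and fitting them costs about 0.1 point if they explain nothing. The lean-obese gap matters more: it is part of the primary aim, it is observational, and no adjusted analysis is named for it. Under modest assumed confounding (0.5 to 1 point) the 5% test rejects 5.7 to 7.7% of the time; higher rates require larger assumed imbalances. The distinction between allocated and BMI-defined groups can be worked out from sections B and D.2, but D.6 does not state it or act on it.

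**What to change.** 1. Make the primary model a linear model of total adherence score on group, sex and age.
2. State in D.6 that obese UF versus obese WMEN is the randomised contrast and that lean WMEN versus obese WMEN is observational.
3. Pre-specify one supporting model for the lean-obese contrast that adds race and SES, but not baseline weight or percent body fat.
4. Do not claim that the sex-and-age model protects the error rate against SES confounding. Only the supporting model addresses it, within the limits of how SES is measured.

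The cost is a change of wording, one extra model and two or three of 57 error degrees of freedom. Precision also falls if the groups differ strongly on the covariates: at R² 0.10 and a 1 SD difference in lean, adjusted power is about 0.76 to 0.77, against 0.83 with no imbalance. No new data are needed: D.6 already names age, sex, race and SES as covariates, and D.4 includes a subjective SES scale.
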